8.3 Rescue Medications

Patients who have bleeding, have platelets drop after initial response, or who do not respond to the therapy may require rescue medications. Use and choice of rescue medications, at protocol specified dosing, is at the discretion of the investigator.

Standard therapies as described will be allowed for use as rescue medications prior to week 12, and the patient may stay on protocol. *If patients have an initial response to a therapy but response wanes, they may be treated again with the same therapy, and this 2nd administration will be considered to be a rescue therapy.* If additional therapies other than the three medications listed are required prior to week 12, patient will be required to come off protocol therapy (but will continue on study).

Rescue medications may be used multiple times, but a separate form must be submitted for each episode.

IVIg: IVIG 1 g/kg x1 (no steroids for pre-medication or adjunctive therapy)

Steroids: Prednisone/Prednisolone 4 mg/kg/day (Max 120 mg/day) x 4 days

Anti-D: Anti-D globulin 75 mcg/kg x1

Data will be collected regarding the reason rescue therapies are being used and maximum platelet count after rescue therapy

After week 12, non-responders in the Eltrombopag arm or patients in the standard care arm requiring additional therapies should be treated at the discretion of the investigator. Additional medications administered after week 12 do not require patient to come off protocol but they should be documented on the case report forms (CRFs).

See section 7.1 for additional allowed and prohibited medications and supportive care.

8.4 Packaging and Labeling

Tablets: White, to almost white, round, film-coated tablets without debossing are provided for clinical use, containing eltrombopag olamine equivalent to 12.5 mg, 25 mg, 50 mg, or 75 mg of eltrombopag free acid. Tablets are packaged in HDPE bottles with plastic, induction-seal, child-resistant caps.

Powder for Oral Suspension: The powder for oral suspension (PfOS) is a reddish brown to yellow powder in heat-sealed foil laminate stickpack; a stickpack may also be referred to as a packet or sachet. Depending on dose and formulation availability PfOS contains eltrombopag olamine equivalent to 12.5 or 25 mg of eltrombopag free acid per stickpack/sachet.

The entire contents of the specified number of stickpacks/primary packages is added to the specified amount of water to produce a suspension and the appropriate patient dose is delivered as described in the study procedures manual.

8.5 Supply of Study Drug at the Sites

Novartis will ship eltrombopag directly to the investigational sites. The initial study drug shipment will be shipped after site activation (i.e., all required regulatory documentation has been received by ICON and Novartis and a contract has been executed). Subsequent study drug shipments will be made after site request for resupply.

8.6 Study Drug Accountability

An accurate and current accounting of the dispensing and return of study drug for each subject will be maintained on an ongoing basis by a member of the study site staff. The number of study drug dispensed and returned by the subject will be

recorded on the Investigational Drug Accountability Record. The study monitor will verify these documents throughout the course of the study.

8.7 Measures of Treatment Compliance

Subjects will be asked about treatment compliance at study visits, and number of missed doses will be noted on CRFs. Study drug containers will be returned to the investigational pharmacy at each visit, and pill counts will be performed to confirm reported compliance.

9 STUDY PROCEDURES AND GUIDELINES

EVALUATIONS ¹ WEEK 0-12	SCREENING/DAY 0									UNSCHEDULED VISITS ¹⁰
		72H	W1	W2	W3	W4	W6	W8	W10	
ELIGIBILITY CHECKLIST	x									
PHYSICAL EXAM	x	x ²		x ²				x ²	x	
BLEEDING ASSESSMENT	x	x	x ³	x ³	x			x	x	
TELEPHONE VISIT			x	x						
DEMOGRAPHIC FORM	x									
BASELINE FORM	x									
CONCOMITANT MEDICATIONS	x	x		x			x	x		
OPHTHALMIC ASSESSMENT	x				As needed					
30 DAY FOLLOW-UP ⁴				As needed						
AE/SAE FORM				As needed						
RESCUE MED FORM				As needed						
HRQOL: KIT	x	x		x			x			
HOCKENBERRY FATIGUE SCORE	x	x		x			x			
PROMIS	x						x			
GLOBAL RATE OF CHANGE		x		x			x			
PLATELET COUNT ^{5, 6}	x	x	x	x	x	x	x	x	x ⁶	
CBC ⁵	x				x			x	x	
AST, ALT, TBILI ⁵	x ⁷		x ⁸		x ⁸	x ⁸	x ⁸	x ⁸	x	
DIR COOMBS	x ⁷									
LDH, RETIC ⁵	x ⁷						x			
CREATININE	x ⁷									
PREGNANCY TEST ⁵	x ⁷			x ⁸			x			
FE, TIBC, %SAT FERRITIN ⁵	x ⁷						x			

TREGS ⁹	x	x
SAMPLES FOR BANKING (OPTIONAL)	x	x

¹ 72H time point may occur +/- 24h. Week 1 – Week 4 procedures may occur +/- 72h.

Week 6 – Week 12 procedures may occur +/- 1 week, as long as procedures are separated by at least 1 week:

² Visits may be performed via telehealth when clinically appropriate if necessary for pandemic-related safety or research restrictions

³ Telephone administration of modified Buchanan scale

⁴ Patients will be followed for safety 30 days after the last dose of study treatment

⁵ Local labs (performed at outside lab not associated with ICON site) are acceptable for labs obtained between study visits

⁶ All platelet counts during Week 5 – Week 12 should be reported. Additional platelet measurements between the scheduled Week 6, 8, 10, and 12 measurements should be reported as unscheduled visits.

⁷ May use previously obtained values for screening assessments if done within past 7 days

⁸ Patients on eltrombopag arm only (for duration of eltrombopag administration)

⁹ Performed at central study lab

¹⁰Physical Exam, Bleeding Assessment, Concomitant Medications, Platelet count, and/or CBC to be performed at unscheduled visits when applicable

EVALUATIONS ¹ 4 MOS – 1 YR	4 MOS ²	5 MOS ²	6 MOS	7 MOS ²	8 MOS ²	9 MOS ²	10 MOS ²	11 MOS ²	1 YEAR	UNSCHEDULED VISITS ⁹
PHYSICAL EXAM			x ³				x ³	x		
BLEEDING ASSESSMENT							x	x		
CONCOMITANT MEDICATIONS			x				x	x		
OPHTHALMIC ASSESSMENT					As needed					
AE/SAE FORM					As needed					
RESCUE MED FORM					As needed					
30-DAY FOLLOW-UP ⁴					As needed					

END OF STUDY FORM	x ⁵									
HRQOL: KIT	x									
HOCKENBERRY FATIGUE SCORE	x									
PROMIS	x									
GLOBAL RATE OF CHANGE	x									
PLATELET COUNT⁶	x ⁷	x ⁷	x	x ⁷	x	x				
CBC⁶			x						x	x
AST, ALT, TBILI⁶	x ⁷									
PREGNANCY TEST⁶		x ⁷		x ⁷		x ⁷		x ⁷		
FE, TIBC, %SAT FERRITIN⁶			x						x	
TREGS⁸									x	
SAMPLES FOR BANKING (OPTIONAL)	x									

¹ 6 month procedures may occur +/- 14 days. 1 year procedures may occur +/- 4 weeks

² Timepoint +/- 7 days

³ Visits may be performed via telehealth when clinically appropriate if necessary for pandemic-related safety or research restrictions

⁴ Patients will be followed for safety for 30 days after the last dose of study treatment

⁵ Form should be completed earlier if patient exits study prior to 1 year

⁶ Local labs (performed at outside lab not associated with ICON site) are acceptable for labs obtained between study visits

⁷ Patients on eltrombopag arm only (for duration of eltrombopag administration)

⁸ Performed at central study lab

⁹Physical Exam, Bleeding Assessment, Concomitant Medications, Platelet count, and/or CBC to be performed at unscheduled visits when applicable

All study assessments should be completed for patients enrolled on the study, even if subjects discontinue protocol treatment early (including patients on eltrombopag arm who discontinue eltrombopag due to non-response and patients on the standard therapy arm who receive prohibited therapies during weeks 1-12).

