5.2 Secondary Endpoints

- 5.2.1 Poor bleeding score (binary) at 1, 2, 3, 4 weeks, 12 weeks, and 1 year after study enrollment defined as WHO Bleeding Scale ≥ 2 or Modified Buchanan Scale ≥ 3
- 5.2.2 Cumulative number of rescue therapies required during the first 12 weeks of treatment
- 5.2.3 Platelet response (binary), defined as ≥ 3 of 4 weeks with platelets $>50 \times 10^9/L$ during weeks 6-12 of therapy, but patient required a rescue treatment during weeks 1-2 of study
- 5.2.4 No further need for treatment (binary) after 12 weeks or 6 months of study
- 5.2.5 Treatment response (binary endpoints) at 1 year defined as:
 - **CR** is defined as platelet count $>/= 150 \times 10^9/L$
 - **Primary Remission** at 1 year is defined as CR at 1 year with no second-line agents required and $>/= 3$ months after discontinuing most recent platelet active medication
 - **Disease resolution** at 1 year is defined as CR at 1 year $>/= 3$ months after discontinuing most recent platelet active medication. May have received a second-line therapy, excluding rituximab or splenectomy.
 - **Disease stability** at 1 year is defined as platelets $>/= 50 \times 10^9/L$ but $<150 \times 10^9/L$ $>/= 3$ months after discontinuing most recent platelet active medication.
- 5.2.6 Number of 2nd-line therapies (defined in section 7.2.1) in weeks 13-52
- 5.2.7 Absolute change in percentage of CD4⁺25⁺Foxp3⁺ regulatory T cells from baseline at 12 weeks and 1 year
- 5.2.8 Absolute change in parent proxy-reported KIT overall scores from baseline to 1 week, 4 weeks, 12 weeks, and 1 year after study enrollment (see Appendix A2)
- 5.2.9 Total scale intensity ratings (continuous) from the Hockenberry Fatigue Scale-Parent (FS-P) at 1 week, 4 weeks, 12 weeks, and 1 year (see Appendix A2)
- 5.2.10 Serum iron, TIBC, transferrin saturation, ferritin, MCV, and hemoglobin at 12 weeks, 6 months, and 1 year after study enrollment
- 5.2.11 Safety evaluations as defined by:
 - Abnormal LFTs:
 - ALT $\geq 3x$ ULN in patients with normal baseline
 - ALT $\geq 3x$ baseline or $\geq 5x$ ULN (whichever is lower) in patients with abnormal baseline
 - ALT $\geq 3x$ ULN AND bilirubin $\geq 1.5 \times$ ULN ($>35\%$ direct)

- Incidence of adverse events (see section 9.1.6)
- Incidence of serious adverse events (see section 12.2)

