9.1.5 Bleeding Assessment

An in-person bleeding assessment will be performed at Baseline/Screening, at Study Visits Week 1, Week 4, Week 12, and 1 year, at unscheduled visits, and at early termination when applicable. Assessments will be performed via telehealth if associated study visit is performed remotely due to pandemic-related safety or research restrictions. A telephone bleeding assessment will be performed at weeks 2 and 3. (See Appendix for details of WHO Bleeding Scale and modified Buchanan Scale).

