To address the primary objective, we will first test for normality of the distribution of the proportion of platelet responders. If the assumption of normality is upheld, a one-sided Cochran-Mantel-Haenszel (CMH) test, at alpha=0.025, will be used to compare the proportion of platelet responders between the two arms. If the normality assumption is violated, then a one-sided Fisher's exact test will be used. The monitoring boundaries and levels of significance for the interim and final analyses of the primary endpoint are detailed in Table 16A. If a monitoring boundary is crossed in an interim analysis, an independent Data Safety Monitoring Board (DSMB) will make a non-binding recommendation regarding trial conduct or potential closure. In the final analysis, we will reject the null hypothesis if the upper (efficacy) boundary z-value of 1.99302 is crossed; in that case, it will be reasonable to conclude that the rate of platelet response is significantly greater in patients treated with eltrombopag than standard first-line treatments. Otherwise, we will conclude that there is insufficient evidence to support superiority of eltrombopag over standard first-line treatments. All randomized patients will be analyzed in the ITT analysis.

Selection of platelet measurements for the determination of platelet response.

All platelet counts will be reported, and the four measurements closest in time to Weeks 6, 8, 10, and 12 will be selected for the determination of the primary endpoint. Within a sliding one-week window, only one measurement can be selected. Patients who have <3 platelet measurements due to missing data will be classified as non-responders.

c. Analysis of Secondary Endpoints

Analyses of all secondary endpoints will be performed in the subset of evaluable patients. To determine the effects of missing data, sensitivity analyses will be performed using two approaches: a) assuming missing at random; and, b) assuming missing not at random. For each secondary endpoint, the assumption of normality will be tested. If violated for binary endpoints, a Fisher's exact test will be used. If violated for continuous endpoints, a Wilcoxon rank-sum test will be used.

To address secondary objective 3.2.1, the Cochran-Mantel-Haenszel test will be used to compare the proportion of patients with poor WHO Bleeding Score and poor Modified Buchanan Score between the two arms.

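### At weeks 2 and 3 the schedule names only the modified Buchanan scale, so the WHO-or-Buchanan bleeding endpoint is undetermined for any patient scoring below 3

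*Combined protocol and SAP*

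**What the plan says.** Section 5.2.1 sets the endpoint and its times: "Poor bleeding score (binary) at 1, 2, 3, 4 weeks, 12 weeks, and 1 year after study enrollment". A patient counts as poor when either the WHO grade reaches 2 or the modified Buchanan score reaches 3. Objective 3.2.1 uses the same two cut-offs and the same six times.

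Section 9.1.5 describes how bleeding is assessed. Week 1, week 4, week 12 and 1 year are in-person assessments (telehealth is allowed under pandemic restrictions). For the other two times, "A telephone bleeding assessment will be performed at weeks 2 and 3". The section closes with a general pointer, "See Appendix for details of WHO Bleeding Scale and modified Buchanan Scale".

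In the section 9 schedule, footnote 3 is attached to two of the bleeding assessments and reads "Telephone administration of modified Buchanan scale". Section 9.1.5 identifies these as weeks 2 and 3.

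For objective 3.2.1, section 16.c plans a Cochran-Mantel-Haenszel test to "compare the proportion of patients with poor WHO Bleeding Score and poor Modified Buchanan Score between the two arms". On missing data for secondary endpoints it says: "To determine the effects of missing data, sensitivity analyses will be performed using two approaches". The two approaches are missing at random and missing not at random.

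**The concern.** An either/or endpoint needs both components before anyone can be classed as negative. At two of its six times the schedule names one component only. If the calls follow footnote 3, the analyst at weeks 2 and 3 will hold a Buchanan score and no WHO grade, and the plan has no rule for that case. The likely improvisation is to score on Buchanan alone, which changes the endpoint's definition at those two times without saying so.

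Section 16.c does not settle the matter. It joins the scales with a different conjunction from 5.2.1 and leaves open whether there is one test or two. At stake is whether the first-listed secondary endpoint can be reported as defined at all six times.

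**Working it through.** The plan states no figure for the bleeding endpoint, so there is nothing to reproduce. The check is a truth table, followed by the size of the under-count.

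**Inputs.** Definition and times: section 5.2.1. Scale named at weeks 2 and 3: section 9 schedule, footnote 3, with section 9.1.5 for the timing. Planned test: section 16.c. Grade descriptions: Appendix A1.

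**Step 1. The composite in 5.2.1, case by case.**

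| Buchanan | WHO | Composite (either/or) |
|---|---|---|
| ≥3 | ≥2 | poor |
| ≥3 | <2 | poor |
| ≥3 | not recorded | poor |
| <3 | ≥2 | poor |
| <3 | <2 | not poor |
| <3 | not recorded | **undetermined** |

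With WHO absent, a positive can be assigned but a negative cannot. Without further assumptions, the proportion poor in an arm is known only to lie between P(Buchanan ≥3) and 1.

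**Step 2. What each reading of 16.c leaves at weeks 2 and 3.**

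| Reading of 16.c | Available | Not available |
|---|---|---|
| One composite, either scale poor | positives (Buchanan ≥3) | status of everyone with Buchanan <3 |
| Two scale-specific tests | Buchanan test, at all 6 times | WHO test, at 2 of 6 times |
| Both scales must be poor | negatives (Buchanan <3) | status of everyone with Buchanan ≥3 |

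Every reading leaves a gap, but not the same one. Under separate testing the Buchanan comparison is intact.

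**Step 3. Size of the under-count if Buchanan alone is used.** Let b = P(Buchanan ≥3) and w = P(WHO ≥2 and Buchanan <3). Then the composite rate is b + w, the Buchanan-only rate is b, and the under-count is w. The documents give neither b nor w. The values below are assumptions for illustration.

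| b (assumed) | w = 0 | w = 5% | w = 10% | w = 20% | Buchanan alone |
|---|---|---|---|---|---|
| 5% | 5% | 10% | 15% | 25% | 5% |
| 10% | 10% | 15% | 20% | 30% | 10% |
| 20% | 20% | 25% | 30% | 40% | 20% |

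**Step 4. Is w likely to be large?** That depends on which Buchanan grade is meant, and the plan does not say. WHO grade 2 is mild blood loss. On the Buchanan overall grade, overt mucosal bleeding is already grade 3, so much of WHO grade 2 would plausibly be caught and w could be small. On the site grades, an active nosebleed controlled with under 15 minutes of pressure is epistaxis grade 2. That is below the cut-off, yet could be WHO grade 2, so w could be larger. The Appendix labels its scale Buchanan rather than modified Buchanan, which does not help to settle the point.

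**Step 5. Between arms.** The composite difference equals the Buchanan-only difference plus (w in the eltrombopag arm minus w in the standard arm). Both arms have the same telephone procedure, and the documents give no basis for a sign or size of that last term.

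**The case against.** Four points can fairly be made on the other side.

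- **The WHO grade may be intended on the call.** Footnote 3 names the Buchanan scale but does not exclude WHO, and section 9.1.5 closes by pointing to both scales. This stands as a doubt about intent. It does not remove the mismatch: the pointer covers all bleeding assessments, in person included, whereas the footnote is the specific instruction for the calls. If both scales were meant, the footnote still needs correcting.
- **The plan may intend two scale-specific comparisons.** Objective 3.2.1 speaks of scores in the plural with one cut-off each, and 16.c names each scale. On that reading the Buchanan result is complete and only WHO is missing at two times. The singular binary endpoint in 5.2.1 favours the composite. The text is ambiguous, which is itself part of the point.
- **Missing-data methods are planned.** They are generic. They give no rule for a component that the schedule does not call for in any patient at a given time.
- **The under-count may be small.** This stands, as step 4 shows, if the overall grade is used.

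A reader might also infer that the endpoint cannot be computed at all at weeks 2 and 3. The documents do not support that: Buchanan ≥3 settles the composite as poor, and the Buchanan comparison is available if the scales are tested separately. A reader might further infer that bleeding will appear to fall after week 1 and rise at week 4 for measurement reasons. Someone comparing rates across visits should be wary, but 16.c plans comparisons between arms and no trend over time for bleeding.

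**Conclusion.** The mismatch is real and of limited reach. Taking footnote 3 at its word, the endpoint in 5.2.1 is undetermined at two of six times for every patient with Buchanan <3. Scoring on Buchanan alone would under-count by w, which the documents do not give. With b assumed at 10% and w between 0 and 20%, the composite would be 10% to 30%, against 10% from Buchanan alone. Separately, 16.c does not say whether one composite or two scale-specific outcomes are tested.

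It would be wrong to read this as a bias in favour of either arm: the same call is used in both, and none is shown. The primary endpoint, sample size and error rate are untouched. The conclusion rests on footnote 3 describing everything collected on the calls. If sites do record WHO there, only the footnote and 16.c need correcting.

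**What to change.** Record the five-level WHO grade in the week 2 and 3 calls that are already scheduled, and amend footnote 3 to name both scales. The endpoint can then be determined at all six times. The cost is one extra item per call.

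If that is not done, define the endpoint as Buchanan ≥3 at all six times in 3.2.1 and 5.2.1, and report the WHO-or-Buchanan composite only at weeks 1, 4, 12 and 1 year. This costs only wording, but gives up the WHO component in the common definition.

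In either case, make 16.c test the endpoint that 5.2.1 defines, with any scale-specific comparisons labelled as additional, and state whether the overall or the site grade supplies the Buchanan score. That is a few lines of text.

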10. SAFETY

10.1 Liver Function Monitoring

AST/ALT/Tbili will be monitored every 2 weeks during the first 12 weeks of study, then monthly for patients continuing on eltrombopag. See section 8.2.2.5 for dose modifications

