10.2 Ophthalmic Assessments

Assessment of cataract risk will be completed by investigator at baseline. Patients at elevated risk (due to history of radiation, prolonged steroid use, or diabetes) should be referred to an ophthalmologist for baseline exam. For patients at standard risk, investigator should perform ophthalmologic exam, and if there are any findings of concern for cataracts, patient should be referred to ophthalmologist for baseline exam. For patients continuing on eltrombopag >12 weeks, consider referral to ophthalmologist for monitoring, especially if receiving other medications (such as steroids) contributing to cataract risk.

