11. ADVERSE EVENTS REPORTING AND DOCUMENTATION

11.1 Adverse Events

An adverse event (AE) is any untoward medical occurrence in a clinical investigation of a patient administered a pharmaceutical product and that does not necessarily have a causal relationship with the treatment. An AE is therefore any unfavorable and unintended sign (including an abnormal laboratory finding), symptom or disease temporally associated with the administration of an investigational product, whether or not related to that investigational product.

An unexpected AE is one of a type not identified in nature, severity, or frequency in the current Investigator's Brochure or of greater severity or frequency than expected based on the information in the Investigator's Brochure.

Information regarding occurrence of adverse events will be captured throughout the study. The collection period for all AEs will begin after informed consent is obtained and end after procedures for the final study visit have been completed, or thirty days after the subject takes the last dose of study drug, whichever is later.

The Investigator will probe, via discussion with the subject, for the occurrence of AEs during each subject visit and record the information in the site's source documents. Adverse events will be recorded in the patient CRF. Adverse events will be described by duration (start and stop dates and times), severity, outcome, treatment and relation to study drug, or if unrelated, the cause.

Abnormal laboratory values or test results occurring after informed consent constitute adverse events only if they induce clinical signs or symptoms, are considered clinically significant, require therapy (e.g., hematologic abnormality that requires transfusion or other support), or require changes in study medication(s).

Adverse events that begin or worsen after first dose of study drug should be recorded in the Adverse Events CRF. Conditions that were already present at the time of informed consent should be recorded in the Medical History page of the patient's eCRF. Adverse event monitoring should be continued for at least 30 days following the last dose of study treatment.

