To address secondary objective 3.2.11, the frequency and proportion (with 95% confidence interval) of patients with abnormal LFTs will be calculated. Adverse event rates will be coded by body system and MedDra classification term. Adverse events and serious adverse events will be tabulated by treatment group and will include the number of patients for whom the event occurred, the rate of occurrence, and the severity and relationship to study drug. If a patient experiences the same toxicity multiple times, a patient will be counted only once for a given toxicity at the maximum grade.

d. Analysis of Exploratory Objectives

Exploratory objectives are hypothesis-generating only. Any exploratory findings need to be confirmed in an independent study.

To address the platelet exploratory objectives 3.3.1, a Cochran-Mantel-Haenszel test will be used to compare the proportion of patients between treatment arms with: (1) specific platelet-defined treatment response at 12 weeks, (2) extreme thrombocytosis, and (3) loss of treatment response (in the subgroup of patients who achieved treatment response during the first 12 weeks. Cumulative incidence curves by treatment arm will be created to describe: (1) time to response and (2) time to platelet and bleeding response. Gray's test will be used to compare the cumulative incidence between treatment arms.

To address the patient-reported outcomes exploratory objectives 3.3.2, KIT scores and fatigue scores will be calculated as described. Spaghetti plots will be used to visualize the scores over time per patient by treatment arm. An ANCOVA model will be used to compare the absolute change from baseline at 1 week, 4 weeks, 12 weeks, and 1 year between the two arms.

To analyze the non-survey endpoints of exploratory objective 3.3.3, a Cochran-Mantel-Haenszel test (for categorical outcomes) or an ANCOVA model (for

continuous outcomes, like the cost of therapy) will be used to compare the two arms.

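### Liver tests are scheduled mainly on eltrombopag, so the by-arm adverse event table ascertains laboratory-detected hepatic events unequally and the plan does not say so

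*Combined protocol and SAP*

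**What the plan says.** **Schedule to Week 12 (section 9).** The liver row, "AST, ALT, TBILI ⁵", has a screening entry, five entries with footnote 8, and one final entry without it. Footnote 8 reads "Patients on eltrombopag arm only (for duration of eltrombopag administration".

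**After Week 12.** Section 10.1 has liver tests "then monthly for patients continuing on eltrombopag". The visible liver entry in the 4-month to 1-year schedule has footnote 7, with the same eltrombopag-only wording.

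**How a laboratory value becomes an AE.** Section 11.1 counts an abnormal value only if it causes signs or symptoms, is judged clinically significant, needs therapy, "or require changes in study medication(s"). Section 8.2.2.5 requires eltrombopag to be discontinued at stated ALT thresholds. Section 11.1 also directs collection to events of grade 3 or higher.

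**Analysis.** Section 16.c states: "Adverse events and serious adverse events will be tabulated by treatment group". The table gives patients affected, rate, severity and relationship to drug. Objective 3.2.11 describes abnormal liver tests in eltrombopag patients only, and AEs in both arms. Endpoint 5.2.11 and the 16.c text on abnormal liver tests do not repeat that restriction.

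**The concern.** A transient, symptomless ALT rise is recorded only if blood is drawn while it lasts. Where one arm is sampled more often, its column will show more such events even if the true rates are equal.

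The AE definition adds to this. In a patient on eltrombopag, an ALT at the threshold changes study medication and so qualifies as an AE. Standard therapy is one dose of IVIg or anti-D, or 4 days of steroid (section 8.2.1). A control patient sampled weeks later will usually have no study medication left to change, and the same value must qualify by another route.

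Readers compare the columns of a by-arm table whether or not a test is attached, and AEs and SAEs are also reviewed at both interim analyses. The risk is that a difference in sampling is read as hepatotoxicity, or that a sparse control column is read as evidence of no liver events there.

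**Working it through.** The plan states no figure on this point, so there is none to reproduce. The check counts draws and then asks what they can detect.

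**1. Scheduled post-baseline liver draws to Week 12**

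- Eltrombopag: five draws with footnote 8 plus the final one = 6. This fits two-weekly testing: 84 days / 14 = 6, at weeks 2, 4, 6, 8, 10 and 12.
- Standard: the final draw only = 1.
- The Week 12 heading is missing from the table as extracted. I place the last entry there by row order. The unscheduled-visit footnote (10) does not list liver tests, so the entry is unlikely to belong to that column.
- With the planned 108 and 54 patients: 108 × 6 = 648 draws against 54 × 1 = 54, if everyone attends and all eltrombopag patients stay on drug. Six is a maximum, because the restricted draws stop when eltrombopag stops.

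**2. After Week 12.** Assuming nine monthly draws, an eltrombopag patient who stays on drug has up to 6 + 9 = 15 in the year, against 1 on standard therapy. The second schedule's liver row is also damaged, so this relies on section 10.1 and the visible footnote.

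**3. What those draws can detect (illustration).** Assume one episode per affected patient, onset uniform over days 0-84, lasting *D* days. The documents call earlier elevations mild and reversible (section 2.3) but give no duration.

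- Draws every 14 days: the next draw is never more than 14 days after onset, so every episode with *D* ≥ 14 is found.
- A single draw at day 84: found only if onset falls in the last *D* days, so the probability is *D*/84.

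| *D* (days) | Two-weekly draws | Week 12 draw only (*D*/84) | Ratio (84/*D*) |
|---|---|---|---|
| 14 | 100% | 17% | 6.0 |
| 28 | 100% | 33% | 3.0 |
| 42 | 100% | 50% | 2.0 |
| 56 | 100% | 67% | 1.5 |
| 84 | 100% | 100% | 1.0 |

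These are probabilities of drawing blood during an episode. They are not AE rates.

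**4. From detection to the table.** An episode reaches the 16.c table only if it also meets the section 11.1 definition and is collected under the grade 3 or higher instruction. The modified grading criteria are in the study manual, so the documents do not show what share of threshold ALT values would pass.

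**5. Reading the draws at common time points.** If both arms are read only at Week 12, the detection ratio is 1.0 for every *D* under the same model.

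**6. Conflict within the protocol.** Sections 8.2.2.5 and 10.1 set liver tests every 2 weeks for the first 12 weeks and can be read as covering all patients; footnote 8 limits the same draws to eltrombopag. If all patients are meant, the ratio to Week 12 is 1.0 and the point applies only after Week 12.

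**The case against.** The best case for the plan is that it makes no between-arm liver comparison. Objective 3.2.11 confines the liver-test description to eltrombopag, the AE table is descriptive, and the interim halting rules rest on toxic deaths, intracranial hemorrhages and unprovoked thromboses. Symptomatic events are sought in both arms: "The Investigator will probe, via discussion with the subject, for the occurrence of AEs during each subject visit". The clinical-significance and grade filters remove many mild elevations. All of this stands and limits the point to how one part of a descriptive table is read. It does not make that part comparable, because hepatic AEs still enter the by-arm table and nothing there tells the reader how often each arm was tested.

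A second objection concerns remedies. Moving test-triggered events out of the main table, or comparing arms at Week 12 alone, could hide drug-related elevations that resolved after discontinuation. That is right, and the fix below does neither.

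Two stronger readings are tempting:

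- **A predicted false excess.** From the earlier pediatric rate of fewer than 10%, a reader might assume 8% in both arms and infer a table showing 8% against 1.3-2.7% (8% × 14/84 to 8% × 28/84). The documents do not support this. The rate comes from pediatric patients in eltrombopag trials, nothing supports it for control patients here, and the calculation counts every episode as a tabulated AE.
- **A parallel problem for cataracts.** The follow-up wording is "For patients continuing on eltrombopag >12 weeks, consider referral to ophthalmologist for monitoring", which is optional. At baseline, patients at elevated risk in either arm "should be referred to an ophthalmologist for baseline exam", and the as-needed ophthalmic entry has no arm footnote. At most, the optional follow-up referral is tied to eltrombopag.

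**Conclusion.** The concern holds as a reporting weakness in section 16.c. Liver testing up to Week 12 is scheduled 6 to 1 per patient, then only on eltrombopag, and the AE definition adds to the imbalance through discontinuation. Laboratory-detected hepatic AEs in the by-arm table are therefore unequally ascertained.

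The size in the table cannot be given. Under uniform onset, the detection ratio to Week 12 runs from 6.0 for 14-day episodes to 1.0 for 84-day episodes, before the AE and grade filters. The count rests on the inferred Week 12 column and on footnote 8 prevailing over the broader reading of sections 8.2.2.5 and 10.1.

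The primary endpoint, the hypothesis tests and the interim halting rules are unaffected. A reader should not infer that the by-arm table is itself an error or that a particular false excess will appear.

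**What to change.** In section 16.c:

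1. Keep all AEs and SAEs in the by-arm table. Keep the liver-test description for eltrombopag patients, and state that restriction in 16.c and 5.2.11 as it is in 3.2.11.
2. Add a by-arm summary of the 5.2.11 liver criteria at the common Week 12 draw, with the number tested and the number of liver draws per arm.
3. Flag hepatic AEs found through eltrombopag-only testing, with a note that they are unequally ascertained and are not evidence of a between-arm difference.
4. Show weeks 1-12 and weeks 13-52 separately.
5. Reconcile sections 8.2.2.5 and 10.1 with footnote 8. If the result is common draws before Week 12, extend item 2 to them.

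The cost is SAP wording and one added table from data already scheduled, with no extra tests or visits. The flag needs a rule fixed in advance, because the AE descriptors in section 11.1 do not include how an event was found. That section dates laboratory AEs by sample collection, so matching to draw dates should serve for most; draws prompted by symptoms may need a separate indicator.

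The Week 12 comparison is insensitive and can miss elevations that resolved after discontinuation. It supplements the full table and must not replace it.
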